## 2.4.3 Extent of investigational medicinal product exposure and compliance

The extent of IMP exposure and compliance will be presented on the safety population. In addition, the extent of IMP exposure will also be assessed and summarized by actual treatment received (150 mg qw, 200 mg q2w, 150 mg q2w) in LTS11210.

### *Dose reduction*

Per study design, patients can reduce dose due to safety consideration. These patients who were switched to a lower dose regimen (ie. 150 mg q2w) due to safety consideration, not administration errors, will be listed and/or summarized separately. There are 3 type cases of dose reduction: initial 150 mg qw reduced to 150 mg q2w, initial 200 mg q2w reduced to 150 mg q2w, initial 150 mg qw switched to 200 mg q2w (per Protocol Amendment 3) then reduced to 150 mg q2w. The reasons for dose reduction are collected and the summary will be provided accordingly. In addition, time to first dose reduction will be analyzed using Kaplan-Meier method for each type of dose reduction by previous treatment prior to enrollment into LTS11210. The maximal grade of neutropenia and maximal grade of ALT elevation after dose reduction will be summarized for each type of dose reduction by dose reduction reason. Treatment discontinuation after dose reduction, such as discontinuation reason and time from dose reduction date to treatment discontinuation date, will also be analyzed by summary and Kaplan-Meier plot. Detailed analyses will be performed in the integrated summary of safety (ISS) and the final CSR.

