### 11.1 TEMPORARY TREATMENT DISCONTINUATION WITH INVESTIGATIONAL PRODUCT(S)

Temporary treatment discontinuation may be considered by the Investigator because of suspected AEs eg, suspected malignancy or because of abnormal laboratory values.

The following is a list of criteria for temporary discontinuation. This list is not exhaustive and IMP may be temporarily discontinued for additional reasons based on Investigator judgment:

- Increase in ALT level  $\geq 3$  x ULN to  $\leq 5$  x ULN and bilirubin  $\leq 2$  x ULN (unless the patient has documented Gilbert's disease). The IMP can be resumed at the dose of 150 mg q2w only after the ALT has returned to a value  $< 3$  ULN and all requirements for resumption of study drug administration are met (see [Section 10.2.4](#) and [Appendix L](#)).
- Decrease in neutrophil count to a level between 500/mm^3 to  $< 1000$ /mm^3 without signs and symptoms of a potential infection. The IMP can be resumed at the dose of 150 mg q2w only after the neutrophils have returned to a value  $\geq 1000$ /mm^3 and all requirements for resumption of study drug administration are met (see [Section 10.2.5](#) and [Appendix L](#)).
- Decrease in platelet count to between 50 000 cells/mm^3 to  $< 100$  000 cells/mm^3 without spontaneous bleeding. The IMP can be resumed at the dose of 150 mg q2w only after the platelet count is  $\geq 100$  000/mm^3 and all requirements for resumption of study drug administration are met (See [Section 10.2.6](#) and [Appendix L](#)).
- Infections requiring oral or parenteral treatment with antibacterial, antiviral and/or antifungal agents (See [Section 10.2.1](#) for additional guidance)
- Surgery requiring temporary treatment discontinuation of biologic DMARD as per applicable guidelines

If the dose is reduced to 150 mg q2w the reduced dose will be maintained for the whole duration of the treatment period.

The IMP can be temporarily discontinued for  $\leq 59$  days (3 IMP doses can be missed).

Reinitiation of treatment with the IMP will be done under close and appropriate clinical/and or laboratory monitoring.

If the restart of the IMP occurs later than 38 days since the last IMP dose (2 IMP doses were already missed), the IMP has to be administered at the study site and the patient to be observed for 30 minutes for any medical events.

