## **11.2 PERMANENT TREATMENT DISCONTINUATION WITH INVESTIGATIONAL PRODUCT(S)**

Permanent treatment discontinuation is any treatment discontinuation associated with the definitive decision from the Investigator or the patient not to re-expose the patient to the IMP at any time.

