### **11.2.1 List of criteria for definitive treatment discontinuation**

The patients may withdraw from treatment with IMP if they decide to do so, at any time and irrespective of the reason, or this may be the Investigator's decision. All efforts should be made to document the reasons for treatment discontinuation and this should be documented in the e-CRF.

Study drug will be permanently discontinued in case of the following events:

- Confirmed diagnosis of opportunistic infection based on the investigator's assessment following diagnostic workups and expert consultations
- Active tuberculosis:
  - the diagnosis can be made either on symptoms or on a chest radiograph suggestive of active TB. Patients should be referred to appropriate medical specialists and whenever possible, culture confirmation of disease should be obtained and recorded in the e-CRF.
- The patient is at risk through close contact with a person with active TB and the patient refuses to undergo TB evaluation.
- Culture positive for non-tuberculosis mycobacteria
- Symptoms of systemic hypersensitivity or anaphylactic reactions.
- Severe neurologic disease such as demyelinating disease or PML.
- Significant laboratory abnormalities:
  - ALT > 5xULN or ALT > 3xULN with concomitant total bilirubin > 2xULN (unless patient with documented Gilbert's syndrome)
  - neutrophil count < 500/mm^3, or neutrophil count < 1000/mm^3 with evidence of infection

- platelet count  $<50\,000/\text{mm}^3$ , or platelet count  $<100\,000/\text{mm}^3$  with evidence of bleeding (see [Section 10.2](#)).
- Conversion to HIV positive status
- Acute renal failure
- Pregnancy in female participant.
- Use of any biologic DMARDs other than IMP, or use of any JAK inhibitor
- For EFC13752 patients: use of any non-biologic DMARDs
- Any adverse events, per investigator judgment, that may jeopardize the patient safety.

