### **2.4.4.3 Analyses of laboratory variables**

The summary statistics (including number, mean, median, standard deviation, minimum and maximum) of all laboratory variables (central laboratory values and changes from baseline) will be calculated for each visit or study assessment (baseline, each post baseline time point, and endpoint) by treatment received. This section will be organized by biological function as specified in [Section 2.1.3.3](#).

The incidence of PCSAs (list provided in [Appendix C](#)) at any time during the TEAE period will be summarized by biological function and treatment received whatever the baseline level and/or according to the following original baseline status categories:

- Normal/Missing
- Abnormal according to PCSA criterion or criteria

The incidence of abnormal laboratory values at any time during the TEAE period will be summarized in shift tables by biological function and treatment group whatever the baseline level and/or according to the following original baseline status categories:

- Normal/Missing
- Abnormal high according to the normal range
- Abnormal low according to the normal range

In addition, for all laboratory parameters, the mean change from baseline at each scheduled visit during the double-blind treatment period will be plotted by treatment groups.

Time to onset of the first G3 or G4 neutropenia (absolute neutrophil count <1.0 Giga/L) in LTS11210, and time to onset of the first platelet count <100 Giga/L in LTS11210 will be analyzed using Kaplan-Meier estimates, using the midpoint of the time interval between the first assessment showing the elevation and the previous assessment, presented by previous treatment prior to enrollment into LTS11210. Further analyses will be in the report of integrated summary of safety.

Listings will be provided with flags indicating the out-of-range values as well as the PCSA values.

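### Time to first dose reduction is planned as Kaplan-Meier with no censoring rule; if early discontinuations and deaths are censored, the curve overstates the proportion of patients whose dose is reduced

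*SAP*

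**What the plan says.** SAP 2.4.3, under Dose reduction, distinguishes three types of reduction to 150 mg q2w: directly from an initial 150 mg qw, from an initial 200 mg q2w, and "initial 150 mg qw switched to 200 mg q2w (per Protocol Amendment 3) then reduced to 150 mg q2w". It then plans that "time to first dose reduction will be analyzed using Kaplan-Meier method for each type of dose reduction", split by the treatment received before LTS11210. It does not say when a patient is censored or who is at risk for each type. Neither document mentions competing risks or a cumulative incidence function.

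Protocol 11.2 defines permanent discontinuation as a "definitive decision from the Investigator or the patient not to re-expose the patient to the IMP at any time". Protocol 11.2.1 opens its list of mandatory reasons with "Study drug will be permanently discontinued in case of the following events"; the list includes "ALT > 5xULN or ALT > 3xULN with concomitant total bilirubin > 2xULN". Protocol 11.1 describes the reduction itself, and says "If the dose is reduced to 150 mg q2w the reduced dose will be maintained for the whole duration of the treatment period", so a patient has at most one reduction.

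SAP 2.2 separately tabulates patients with dose reductions as a number and a percentage of all enrolled patients. SAP 2.4.4 describes the safety analyses as descriptive, with no routine testing.

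**The concern.** Kaplan-Meier treats a censored patient as someone who could still have the event later, at the same rate as those who remain under observation. That does not fit a patient who has permanently stopped sarilumab or died, because no reduction can follow. Premature permanent discontinuation and death are therefore competing events. For reduction directly from 150 mg qw there is a third: once a patient is switched to 200 mg q2w, any later reduction counts as a different type.

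If these patients are censored, 1-KM is too high as an estimate of the proportion reduced by a given week, and the excess accumulates over 264 to 516 weeks of treatment. Reading the curve as what would happen if nobody stopped does not fully help. ALT, neutrophils and platelets drive both reduction and, at worse values, permanent discontinuation (Protocol 11.1 and 11.2.1), so censoring at discontinuation is unlikely to be independent of the risk of reduction.

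What is at stake is a descriptive tolerability figure in the clinical study report, which may not match the crude percentage reported for the same event.

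**Working it through.** The plan gives no figure to reproduce and no event rates. All hazards below are assumptions; only the horizon and the group-size bound come from the documents.

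**Inputs**
- Horizon: 264 weeks = 5.06 years (Protocol 6.2).
- Reduction hazard: a per year for the first 0.25 year, then b per year (assumed).
- Premature permanent discontinuation, including death: d per year, constant (assumed).
- Largest possible active-control group: 168 (SFY13370) + 7 (ACT11575) = 175 (SAP 1.3). This counts every patient from the two studies, so the real group is smaller.

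**Formulas at 5.06 years** (remaining time 5.06 − 0.25 = 4.81)
- 1-KM, discontinuers censored: 1 − exp[−(0.25a + 4.81b)].
- True cumulative incidence (CIF): a/(a+d) × [1 − exp(−0.25(a+d))] + exp(−0.25(a+d)) × b/(b+d) × [1 − exp(−4.81(b+d))].

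**Mildest case** (a = 0.20, b = 0.02, d = 0.06)
- 1-KM = 1 − exp(−0.146) = 13.6%.
- CIF = 0.769 × 0.0629 + 0.937 × 0.25 × 0.319 = 0.048 + 0.075 = 12.3%.
- Excess 1.3 points.

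**Middle case** (a = 0.20, b = 0.04, d = 0.10)
- 1-KM = 1 − exp(−0.242) = 21.5%.
- CIF = 0.667 × 0.0723 + 0.928 × 0.286 × 0.490 = 0.048 + 0.130 = 17.8%.
- Excess 3.7 points.

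**Heaviest case** (a = b = 0.05, d = 0.15)
- 1-KM = 1 − exp(−0.253) = 22.4%.
- CIF = 0.25 × [1 − exp(−1.012)] = 15.9%.
- Excess 6.4 points before rounding.

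**Dependence on timing.** Three further scenarios were simulated, each with about 38% to 41% discontinuing before any reduction:
- Flat hazards: 22.4% against a true 17.0%.
- Early reductions, flat discontinuation: 24.9% against 21.5%.
- Early reductions, late discontinuation: 17.7% against 16.6%.

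The direction is the same each time. The size depends on how many patients stop while reductions are still occurring.

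**Wider range.** With proportional hazards, if R is the true proportion reduced and D the proportion discontinuing first, 1-KM = 1 − (1 − R − D)^(R/(R + D)). R = 10%, D = 20% gives 11.2% (+1.2 points). R = 20%, D = 40% gives 26.3% (+6.3). Over R from 5% to 30% and D from 10% to 50% the excess runs from 0.3 to 15.3 points; the top end needs both values at their maximum.

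**Against sampling error.** Greenwood standard error of 1-KM in the mildest case, taking the whole group as at risk for the type: 1.62 points at n = 500, so the excess is 1.28/1.62 = 0.79 standard errors; 2.75 points at n = 175, so 1.28/2.75 = 0.47 standard errors.

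**The case against.** **The curve need not be read as a proportion.** The SAP does not name a proportion reduced at Week 264 as the target. Kaplan-Meier with censoring at discontinuation describes the reduction rate among patients still on drug, which is a legitimate descriptive quantity, and SAP 2.2 gives the crude percentage without this bias. This stands in part and lowers the importance of the point. However, the crude percentage gives no time curve and does not allow for unequal follow-up, and the SAP does not say which quantity the curve is meant to show.

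**Kaplan-Meier does not force censoring at discontinuation.** A reader might infer that it does. In fact, keeping discontinuers in the risk set until their administrative end date would remove the bias. The SAP does not say this is done, so the overstatement is conditional on usual practice and the missing rule is part of the problem.

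**The same criticism might seem to apply to the neutrophil and platelet curves.** SAP 2.4.4.3 says that time to the first neutrophil count below 1.0 Giga/L and the first platelet count below 100 Giga/L "will be analyzed using Kaplan-Meier estimates, using the midpoint of the time interval between the first assessment showing the elevation and the previous assessment". The extension is not supported. Stopping sarilumab does not prevent either event. The treatment-emergent period runs to 60 days after the last dose (SAP 2.1.3), and haematology is taken at the end-of-treatment visit (Protocol 12.1.12). The neutrophil and platelet values that require discontinuation in Protocol 11.2.1 already meet the event definition. Treating discontinuation as a competing event there would lose first events found after the last dose.

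**Comparisons across previous-treatment groups are not invalidated.** No test is planned. If discontinuation differs between groups the upward bias differs too, but cumulative incidence has its own limit: a group that stops more often will show fewer reductions.

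**Conclusion.** The point holds for the dose-reduction curves in SAP 2.4.3 only. If premature permanent discontinuations and deaths are censored, 1-KM overstates the proportion of patients whose dose is reduced. The direction follows from the protocol's own definition of permanent discontinuation. The size rests entirely on assumed rates: about 1 to 6 points at Week 264 in the main cases, less when reductions come early or few patients stop, and more only when both reductions and discontinuations are frequent.

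A reader might infer that the excess always matters against sampling error. It does not: at 175 patients the mildest case gives less than half a standard error, and curves split by type and previous treatment can be based on fewer.

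Completion per protocol (commercial availability, the 2020 closure, Week 264 in the UK) is ordinary administrative censoring and causes no such bias. Because the analysis is descriptive and the crude percentage is also reported, this is a minor, cheap improvement.

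**What to change.** In SAP 2.4.3:
- Replace Kaplan-Meier for time to first dose reduction with the Aalen-Johansen cumulative incidence, with premature permanent discontinuation and death as competing events.
- For the curve of reduction directly from an initial 150 mg qw, add the programme-wide switch to 200 mg q2w as a further competing event.
- State for each type who is in the risk set and from when.
- Censor only at per-protocol end of treatment or data cut-off, and say so.
- Keep Kaplan-Meier for time from dose reduction to all-cause treatment discontinuation, where discontinuation is itself the event.

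Leave the neutrophil and platelet curves in 2.4.4.3 as they are on this point.

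The cost is a few lines of SAP text and a standard software option, with no new data. The downside is that reported proportions will be slightly lower and will reflect discontinuation as well as reduction, so they no longer describe the on-drug reduction rate alone; a footnote should say this.

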### **2.4.3.1 Extent of investigational medicinal product exposure**

The extent of IMP exposure will be assessed by the duration of IMP exposure and actual dose information.

#### ***Extent of IMP exposure***

Due to a global switch to the pivotal dose or a dose reduction to a lower pivotal dose if it applies, each patient may receive multiple doses. Hence the duration of IMP exposure will be calculated under 'sarilumab' treatment regardless what doses the patient received during LTS11210.

For patients receiving weekly injections at the time of last injection, duration of IMP exposure is defined as: [Date of last injection of the study medication in LTS11210] – [Date of first injection of the study medication in LTS11210] + 7 day, regardless of unplanned intermittent discontinuations (see [Section 2.5.3](#) for calculation in case of missing or incomplete data).

For patients receiving biweekly injections at the time of last injection, duration of IMP exposure is defined as: [Date of last injection of the study medication in LTS11210] – [Date of first injection of the study medication in LTS11210] + 14 day, regardless of unplanned intermittent discontinuations (see [Section 2.5.3](#) for calculation in case of missing or incomplete data).

#### ***Duration of each dose***

Period for each treatment dose received is calculated as the days from the starting (injection) date of that dose regimen to one day before the starting date of the following dose regimen or to the end (injection) date of the same dose + 14 days (7 days for patients receiving weekly injections only) if that is the last dose regimen in the study. Duration of IMP exposure will be summarized descriptively as a quantitative variable (number, Mean, SD, Median, Minimum, and Maximum). In addition, duration of treatment exposure will also be summarized categorically by counts and percentages for each of the following categories and cumulatively according to these categories: ≤4 weeks, >4 and ≤12 weeks, >12 and ≤24 weeks, > 24 and ≤48 weeks, > 48 and ≤72 weeks, >72 and ≤96 weeks, and at 24-week intervals through the end of the study.

Additionally, the cumulative duration of treatment exposure, defined as the sum of patients' duration of treatment exposure and expressed in patient years, will be provided.

### **2.4.3.2 Compliance**

A given administration will be considered as non-compliant if the patient did not take the planned dose of treatment as required by the protocol. No imputation will be made for patients with missing or incomplete data.

Percentage of compliance for a patient will be defined as the number of administrations (injections) the patient was compliant divided by the total number of administrations (injections) the patient was planned to take during the treatment epoch (ie, from the 1st to the last administration).

Treatment compliance percentages will be summarized descriptively as quantitative variables (Number, Mean, SD, Median, Min, and Max). The percentage of patients whose compliance is <80% will be summarized. In addition, patients with the wrong dose or an overdose will be summarized.

Cases of overdose (administering 2 or more sarilumab doses in less than 11 calendar days) will be listed as such. More generally, dosing irregularities are listed in [Section 2.2.1](#).

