Investigational Medicinal Product(s)  Formulation	
Sarilumab (anti-Interleukin 6R<math>\alpha</math> monoclonal antibody (Anti-IL6R<math>\alpha</math> mAb)
 
Two different pharmaceutical forms are used in the study: C1F2 used in vials and C2F3 (pivotal formulation) used in prefilled syringes.
 
Before Phase 3 pivotal dose selection decision: vials 150 mg (75 mg/ml)
 
After Phase 3 pivotal dose selection decision, and prior to availability of prefilled syringes: vials 150 mg (75 mg/mL), and 200 mg (100 mg/mL)
 
After Phase 3 pivotal dose selection decision, upon availability of prefilled syringes: prefilled syringes filled with 150 mg (131.6 mg/ml) or 200 mg (175 mg/ml) of drug product
 
In the sub-study: prefilled syringes with a needle safety shield (PFS-S) with exactly the same IMP formulation as the PFS used in the main study

Route(s) of administration:	Subcutaneous (SC) injection in the abdomen, thigh, or upper arm Injection volume: 2 mL (vials); 1.14 mL (prefilled syringes)
Dose regimen:	
Before the phase 3 pivotal dose selection decision, the sarilumab dose was 150 mg weekly (qw) (dose reduction to 150 mg q2w in case of neutropenia, thrombocytopenia, or an increase in liver enzymes (ALT).
 
After the phase 3 pivotal doses were selected; the sarilumab dose is 200 mg q2w and the reduced dose is 150 mg q2w.
 
Note: Patients enrolled in the study prior to the dose selection decision and receiving 150 mg qw were switched to 200 mg q2w. Patients who prior to the dose selection decision were assigned to the step-down dose of 150 mg q2w because of a safety issue continued to receive sarilumab 150 mg q2w.

Noninvestigational Medicinal Products (except EFC13752 patients)	
One or a combination of non-biologic disease modifying drugs (DMARDs).
 
Folic/Folinic acid in patients using MTX.
 
Formulation, route of administration and dose regimen should follow the applicable local labeling information.

PRIMARY AND SECONDARY ENDPOINT(S)	
Primary endpoint: Safety assessment of sarilumab over time.
 
Secondary Endpoint(s):
 
 
• The proportion of patients who achieve American College of Rheumatology criteria ACR20/ACR50/ACR70, DAS28 (Disease activity score) Remission, and EULAR (European League against Rheumatism) Response over time.
 
• DAS28-CRP over time
 

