## 8 STUDY TREATMENTS

### 8.1 INVESTIGATIONAL MEDICINAL PRODUCT

- Pharmaceutical form: the pharmaceutical form of sarilumab has been modified since the initial version of the study protocol. Sarilumab, in vials (formulation C1F2), was dispensed to all patients enrolled into the study prior to the phase 3 dose selection decision. Thereafter, drug product in vials has been phased out of the study, and patients have been dispensed with drug product in prefilled syringes (pivotal formulation C2F3) once sufficient quantities were available and appropriate local approvals obtained. For completeness, all IMP formats used during the study are presented here:
  - Currently dispensed IMP for all patients:
    - Sarilumab in prefilled syringe (PFS): Glass syringes with a 27 gauge thin wall, 1/2-inch staked needle, with FM30 needle tip cap (latex free) filled at 1.14 mL with C2F3 drug product at 131.6 mg/mL (150mg dose) or 175 mg/mL (200mg dose). PFS with FM30 needle tip is the only pharmaceutical form dispensed to patients from EFC10832, SFY13370, and EFC13752.
    - Sarilumab in prefilled syringe with safety system (PFS-S) with exactly the same formulation as the PFS with FM30 needle tip cap described above. The PFS-S is used for patients in the sub-study only. Refer to [Appendix R](#) for further details of the safety system.
  - Previously dispensed IMP:
    - Sarilumab in amber glass vials: filled to 2 mL with 75 mg/mL (150mg dose), or 100 mg/mL (200mg dose) of C1F2 drug product
    - Sarilumab in PFS: Glass syringes as described above, but with FM27 rubber needle shield (needle cap may contain dry natural rubber latex)

To ensure that the administration of the investigational product with PFS will minimally deliver the targeted doses of 150 mg and 200 mg, the PFS will contain an 8% average overfill.

- Dose per administration
  - Before the phase 3 pivotal dose regimens were selected:**
    - 150 mg administered weekly or every other week (reduced dose)
  - After the phase 3 pivotal dose regimens were selected:**
    - 200 mg administered every other week or 150 mg administered every other week (reduced dose).
- Route and method of administration: Subcutaneously in abdomen, thigh or upper arm.

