- Lupus like syndrome
- Demyelinating events (including suspicion of PML) or significant unexplained neurological symptoms meeting seriousness criteria
- Gastrointestinal perforation
- Specific cardiovascular events and deaths (see [Section 10.2.10](#)):
  - Myocardial infarction
  - Stroke
  - Hospitalization due to unstable angina
  - Hospitalization due to heart failure
  - Hospitalization due to transient ischemic attack
  - Deaths (cardiovascular and noncardiovascular)

- Pregnancy:
  - Pregnancy occurring in a female patient included in the clinical study (as well as pregnancy occurring in a female partner of a male patient included in the study with IMP/NIMP) will be recorded as a pre-specified AE with immediate notification in all cases. It will be qualified as an SAE only if it fulfills the SAE criteria.
  - In the event of pregnancy in a female patient included in the trial, IMP should be discontinued.
  - The follow-up of the pregnancy in a female participant or in a female partner of a male participant will be mandatory until the outcome has been determined.
- Symptomatic Overdose with IMP/NIMP:
  - An overdose (accidental or intentional) with the IMP is an event suspected by the Investigator or spontaneously notified by the patient and defined as at least twice the dose of IMP during an interval of less than 11 days (NOTE: this definition was less than 6 days for patients on the initial weekly dosing regimen in the study). The circumstances (ie, accidental or intentional) should be clearly specified in the verbatim and symptoms, if any, entered on separate AE forms.
  - An overdose (accidental or intentional) with any NIMP (as defined in [Section 8.2](#)) is an event suspected by the Investigator or spontaneously notified by the patient and defined as at least twice of the intended dose within the intended therapeutic interval. The circumstances (ie, accidental or intentional) should be clearly specified in the verbatim and symptoms, if any, entered on separate adverse event forms.

In addition, the following AESIs/AEPs with immediate reporting must always be considered as medically important if not fulfilling any other seriousness criteria (see [Section 10.4](#)) and reported as serious adverse events.

- Systemic opportunistic infections
- Grade 4 neutropenia lasting for at least 5 days
- Anaphylaxis fulfilling the criteria in [Appendix O](#)

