- Demyelinating events (including suspicion of PML), or significant, unexplained neurological symptoms meeting seriousness criteria
- Gastrointestinal perforation
- Myocardial infarction
- Stroke
- Hospitalization due to unstable angina
- Hospitalization due to heart failure
- Hospitalization due to transient ischemic attack
- Deaths (cardiovascular and noncardiovascular)

For the following AEPM/AESI, the Sponsor **will not** require immediate notification; however if the event meets any seriousness criteria as per the Investigator's judgment, it should be reported as a SAE.

- Neutropenia grade 3 ( $<1000$  and  $\geq 500/\text{mm}^3$ ) without permanent treatment discontinuation (see [Section 10.2.5](#))
- Thrombocytopenia ( $<100\ 000/\text{mm}^3$ ) without permanent treatment discontinuation (see [Section 10.2.6](#))
- ALT elevation  $\geq 3$  x ULN without permanent treatment discontinuation (see [Section 10.2.4](#))
- Confirmed diverticulitis or gastrointestinal ulceration (see [Section 10.2.8](#))
- Significant unexplained neurological symptoms not meeting seriousness criteria (see [Section 10.2.2](#))
- Asymptomatic overdose (definition described above) with IMP/NIMP. The circumstances (ie, accidental or intentional) and the lack of symptoms (ie, asymptomatic) should be clearly specified in the verbatim.

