#### ***Observation period***

The observation period will be divided into 4 epochs:

- The SCREENING epoch is defined as beginning with the last visit in the previous studies to the first dose of IMP in LTS11210
- The TREATMENT epoch is defined as the time from first dose of IMP in LTS11210 to last dose of IMP + 13 days (6 days for patients receiving weekly injections only)
- The FOLLOW-UP epoch is defined as the time from the end of TREATMENT epoch to last dose of IMP + 60 days
- The POST-STUDY epoch is defined as the time after the last dose of IMP + 60 days

The rationale of having “last dose of IMP + 60 days” as the end of follow-up epoch is to capture the events observed within an approximately 5 half-lives of the last IMP. The treatment-emergent AE (TEAE) period will include both TREATMENT and FOLLOW-UP epochs.

Please note: Not all the patients will have all 4 epochs. For example, if a patient died on the 7th day after the last dose of IMP, his/her TREATMENT epoch will be from the first dose of IMP to his/her death date and will have no FOLLOW-UP or POST-STUDY epoch; if a patient had his last visit (i.e. follow-up visit 29) on the 50th day after the last dose of IMP and have no AE reported after this date, his/her FOLLOW-UP epoch will be ended on last dose of IMP+50 days and will have no POST-STUDY epoch.

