**Table 1 - AESI and search criteria**

AESI flag	Searcha criteria
Leukopenia	SMQ: Haematopoietic leukopenia
Thrombocytopenia	SMQ: Haematopoietic thrombocytopenia
Infections (Opportunistic infections, Tuberculosis)	Primary SOC: Infections and infestations (CRF checkbox: Opportunistic infections; HLT Tuberculosis infections)
Hepatic disorders	SMQ : Drug-related hepatic disorders – comprehensive search
Diverticulitis/potential GI perforations b	SMQ: Gastrointestinal perforation and HLT: Diverticulum inflammations
GI ulcerations	SMQ: Gastrointestinal ulceration
Elevation in lipids	SMQ: Dyslipidemias
Anaphylaxis	SMQ: Anaphylactic reaction
Hypersensitivity	SMQ Hypersensitivity
Injection site reactions	HLT Injection site reactions
Malignancy	SMQ: Malignant or unspecified tumours Excluding non-melanoma skin cancer: SMQ Malignant or unspecified tumours excluding HLT of Skin neoplasms malignant and unspecified (excl melanoma)
Lupus-like syndrome	SMQ: Systemic lupus erythematosus
Demyelinating disorders	SMQ: Demyelination
Pregnancy c	CRF checkbox: Pregnancy
Overdose c	CRF checkbox: Symptomatic overdose

a All SMQs are narrow search  b These events will be further reviewed to identify cases of GI perforations  c Standard AESI applies to all Sanofi studies
	

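### The SAP's single 11-day overdose window classes on-schedule weekly injections as overdoses, contrary to the protocol's 6-day window for the weekly regimen

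*SAP*

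**What the plan says.** SAP 2.4.3.2 (Compliance) contains the SAP's only definition of overdose: "Cases of overdose (administering 2 or more sarilumab doses in less than 11 calendar days) will be listed as such". The paragraph before it adds a table: "In addition, patients with the wrong dose or an overdose will be summarized". Neither sentence distinguishes regimens.

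Protocol 10.5.4 does distinguish them. It sets the IMP overdose window at under 11 days and then notes that "this definition was less than 6 days for patients on the initial weekly dosing regimen in the study".

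Weekly dosing did occur in this study. Patients first received 150 mg weekly, and later "Patients enrolled in the study prior to the dose selection decision and receiving 150 mg qw were switched to 200 mg q2w" (protocol synopsis, dose regimen).

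Elsewhere the SAP gives weekly dosing its own rules. The treatment epoch ends 13 days after the last dose, but "6 days for patients receiving weekly injections only" (SAP 2.1.3, Observation period). In SAP 2.4.3.1, exposure adds 7 days for weekly injections and 14 for biweekly ones, and the duration of each dose follows the same pattern. 150 mg qw is also a named exposure category in SAP 2.4.3.

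**The concern.** A rule suited to every-other-week dosing is applied to a period in which correct dosing was weekly. For that period the flag cannot separate a true overdose from a patient injecting exactly as instructed, and the listing and count would report correct dosing as overdose.

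The other overdose output does not replace this one. The AESI category in SAP Table 1 is drawn from "CRF checkbox: Symptomatic overdose", so it covers symptomatic cases only. Protocol 10.5.4 also makes "Asymptomatic overdose (definition described above) with IMP/NIMP" an event to be reported. The Compliance flag is the only overdose-specific output in the SAP not restricted to symptomatic cases. Asymptomatic cases reported as adverse events would otherwise appear only among the general TEAE tables and listings.

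The false cases could also be uneven across columns. SAP section 2 presents results by previous treatment. Among the previous studies whose arms SAP 1.1 lists, only EFC11072 had non-selected sarilumab doses, and it is also the main possible source of weekly-dosed patients. By inference, false overdoses could gather in the column for other sarilumab doses and look like a group difference.

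**Working it through.** **Inputs**
- SAP window, all patients: under 11 calendar days (SAP 2.4.3.2).
- Protocol windows: under 11 days; under 6 days for the initial weekly regimen (protocol 10.5.4).
- Planned intervals: 7 days weekly, 14 days every other week. The minimum permitted every-other-week interval is 11 days (protocol 8.1).

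**Check.** A pair of consecutive injections is flagged if the interval in days is below the window; *n* injections give *n* − 1 intervals.

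| Schedule | Interval | Injections | Flagged, under 11 (SAP) | Flagged, under 6 (protocol, weekly) |
|---|---|---|---|---|
| Weekly, on time | 7 | 12 | 11 of 11 | 0 of 11 |
| Weekly, late (illustration) | 10 | 12 | 11 of 11 | 0 of 11 |
| Weekly, early (illustration) | 4 | 12 | 11 of 11 | 11 of 11 |
| Every other week, on time | 14 | 6 | 0 of 5 | not applicable |
| Every other week, earliest allowed | 11 | 6 | 0 of 5 | not applicable |

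Counting calendar days inclusively makes the weekly interval 8, still below 11. The two rules disagree for weekly intervals of 6 to 10 days. The error runs one way: any interval under 6 days is also under 11, so no true case is lost. After the first 12 injections, each further 12 weeks of on-time weekly dosing adds 12 flagged intervals.

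**Is the weekly window restored elsewhere in the SAP?** No. SAP 2.4.3.2 points onward only to 2.2.1, which concerns kit dispensing. SAP 1.5 and 1.6, which record changes to the statistical plan, do not mention it.

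**How many patients?** The documents do not say, so only bounds are possible.
- Rollovers in SAP 1.1: 1,283 + 7 + 456 + 168 + 111 = 2,025. SAP 1.3 gives 454 for EFC10832, hence 2,023; the difference does not matter here.
- Protocol 8.1 states that "PFS with FM30 needle tip is the only pharmaceutical form dispensed to patients from EFC10832, SFY13370, and EFC13752". The synopsis places prefilled syringes after dose selection, so these three studies contribute no weekly patients.
- Ceiling: 1,283 (EFC11072) + 7 (ACT11575) = 1,290; 1,290/2,025 = 63.7%. It cannot be reached, because EFC11072 Part B Cohort 2 began after dose selection (SAP 1.1).
- Assumption A, exactly the Part A and ACT11575 rollovers had at least two weekly doses: 243 + 7 = 250; 250/2,025 = 12.3%.
- Assumption B, half of those: 125/2,025 = 6.2%.
- Early Part B Cohort 1 patients dosed weekly would add to A or B.

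**The case against.** The strongest objection is that the SAP never says the flag is derived from injection dates. Protocol 10.5.4 treats overdose as something the investigator suspects or the patient reports. If the listing starts from reported cases, on-schedule weekly doses are never candidates. This makes the consequence conditional on programming the rule as written. It does not remove the conflict: the parenthesis in SAP 2.4.3.2 reads as a derivation rule, and a programmer who departed from it would be making an undocumented change.

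Second, the 11-day definition is attached to the listing sentence, not to the summary. That is literally so. It is still the SAP's only overdose definition and sits next to the summary sentence, so it naturally governs both.

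Third, the protocol is equally silent on the interval that spans a regimen change, so that part is a gap in both documents and affects few intervals per patient. This stands; it only needs settling once the rule depends on regimen.

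Fourth, the SAP counts two or more doses where the protocol counts at least twice the dose. Since each administration is one injection (protocol 8.1), the two nearly coincide. They can part at a dose change: 150 + 200 = 350 mg is above 2 × 150 = 300 but below 2 × 200 = 400. This is tidying, not a reason for the finding.

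Finally, weekly dosing is over. That does not help, because the SAP serves the final CSR (SAP section 1) and the safety population is everyone with at least one LTS11210 dose (SAP 2.3.1).

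**Conclusion.** The concern holds. SAP 2.4.3.2 and protocol 10.5.4 give different overdose windows for the weekly regimen, and the SAP's window classes correct weekly dosing as overdose. Followed as written, it lists every patient with two on-time weekly injections. That conclusion needs no assumption about numbers. The count of affected patients is unknown; 125 and 250 are illustrations, and 1,290 is a ceiling that cannot be reached.

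The damage is limited to over-inclusion in one descriptive listing and its summary. The percentage-compliance calculation is untouched because it counts planned administrations taken. The AESI overdose category comes from a CRF checkbox, and the primary endpoint does not use this flag. It is worth correcting before the final report because, for time on 150 mg weekly, the output would carry no usable information about overdose.

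**What to change.** Reconcile SAP 2.4.3.2 with protocol 10.5.4 by making the overdose flag depend on the regimen in force at each injection, using the two windows the protocol already states. Key the condition on dosing frequency and not on dose strength, because 150 mg was given both weekly and every other week.

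State which window applies to the interval spanning a change from weekly to every-other-week dosing. SAP 2.4.3 shows two routes: the general switch to 200 mg q2w, and reduction from 150 mg qw to 150 mg q2w. Say that the same definition governs the listing and the summary, and use one wording for the dose criterion in both documents.

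The cost is one or two SAP sentences and one programming condition. Regimen start dates are already needed for the duration of each dose in SAP 2.4.3.1, so no new data are required.
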